This gives us two equations in two unknowns, and allows us to estimate the true cumulative incidence of both infections  $\pi_Z$ ,  $\pi_D$  from the observed seroprevalences  $p_Z$ ,  $p_D$ .

To bring together cumulative incidence estimates from multiple tests, the above methods for correcting for sensitivity and specificity can be extended to apply to *any number of tests*, and *any number of combinations of tests* (see Appendix 6).

**8.1.3** Proportion of symptomatic infections. For each infection, the denominator is the number of infected women, and numerator is the number of those reporting symptoms (according to pre-specified criteria) who were confirmed by PCR+, IgM+, or rising IgG. Infections which may either be ZIKV or DENV will be tabulated separately. We will investigate whether the proportion of symptomatic infections for each arbovirus is related to seroprevalence of the others.

8.1.4 Seroconversions and incidence of primary infections. The denominator is the number of women who were initially IgG- and who were retested on IgG at a later date. The numerator is the number of these women who were tested IgG+ at some later date. The time at risk is the total time between the first IgG- and either the first IgG+ if there was one, or the time between the first and last IgG- tests. Incidence of primary infection is found by dividing the number of seroconversions by total time at risk.

Once again, both crude and sensitivity-specificity-adjusted estimates will be considered, and separate estimates will be derived if there is more than one IgG test, using a similar format to *Table 5*.

Associations between incidence on one arbovirus and previous infections with the same or other arboviruses will be explored

8.1.5 IgM prevalence. The denominator is the number of women who were ever tested by IgM, and the numerator is the number whose first IgM test was a +ve. Separate analyses will be performed for different IgM tests, or tests on different samples.

Sensitivity and specificity will be taken into account, as above, and so will ZIKV-DENV cross-reactivity, to give adjusted estimates of IgM prevalence for each assay. Associations between IgM prevalence on one arbovirus and previous infections with the same or other arboviruses will be explored.

Author: [name] (UNIVBRIS)

27

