8.1.6 Incidence of primary infections estimated by increase in seroprevalence. If we know or can estimate the cumulative incidence at a starting point T, then cumulative incidence at time t is related to incidence between t and T as follows:

$$\pi(t) = \pi(T) + (1 - \pi(T) \left( 1 - \exp\left( -\sum_{T \le u \le t} \lambda(u) \right) \right)$$

This can be modelled, for example assuming piece-wise constant incidence.

For DENV infection, which has been present for much longer, it may be preferable to model age-and time-specific cumulative incidence:

$$\pi(a,t) = \pi(a,T) + (1-\pi(a,T)\left(1-\exp\left(-\sum_{T \le u \le t} \lambda(a-T+u,u)\right)\right)$$

Using data from pregnant women, we would model incidence from time T and age 16 upwards.

These calculations assume that cumulative incidence can be estimated by adjusting seroprevalence for sensitivity and specificity as shown in *Section 8.1.2* 

8.1.7 Alignment with surveillance data: population estimates of incidence. Once estimates of incidence are available, they can be aligned with surveillance reports to estimate the proportion of incident infections (symptomatic or not) that are reported to the surveillance system. "Alignment" should be interpreted as putting the dates of the tests on the real timescale, so that incidence estimates for ZIKV, DENV, and CHIKV based on ZIKA-VT data can be compared to numbers of cases notified to national or regional surveillance centers, both confirmed and suspected.

If the estimated incidence in some period t is  $\lambda(t)$  and M(t) cases are reported in, say, the population of adult women aged 16-44, over the same time period and from the same area where ZIKA-VT is recruiting, then we can calculate the proportion of all infections that were reported over that time period as :

$$\theta(t) = \frac{M(t)}{N(1 - e^{-\lambda(t)})}$$

Where N is the relevant population size. This quantity can be examined over time to see if it remains relatively stable, and can be used in analyses of test persistence and adjustments for sensitivity and specificity needed to estimate the gestational age of maternal infection and vertical transmission rate (see Sections 5,7).

Further, once an estimate  $\theta(t)$  is available, it can be used to "gross-up" counts M(t), to estimate the true number of infections on a national or regional basis:  $M(t)/\theta(t)$ .

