#### 8.2 Analyses of properties of diagnostic tests

As noted earlier the ZIKA-VT and ZIKA-VID programs are inter-related and the analyses set out in *Section 7.5* will provide the definitive information on the persistence of IgM and other tests.

However, the population epidemiology data collected by ZIKA-VT also provides an opportunity for *supportive* analyses of test persistence, sensitivity and specificity. Results should be compared with the more formal evaluations undertaken as part of ZIKA-VID, which will comprise evidence from published literature as well as findings from *de novo* field work.

8.2.1 Average persistence of IgM. Given estimates of IgM prevalence (section 8.1.5) and incidence of primary infections based on seroconversion (section 8.1.4) or changes in cumulative incidence (section 8.1.6), estimates of the average persistence of IgM can be estimated by dividing IgM prevalence by IgM incidence.

We anticipate that IgM persistence may differ in women with previous ZIKV or DENV infections. If these women can be identified by avidity tests it will be possible to generate separate estimates of average IgM persistence for primary and secondary infections

8.2.2 Sensitivity and cross-reactivity of IgM and IgG tests. Estimates of sensitivity will be available for IgM and IgG tests in women with infections confirmed by PCR, and from cases where tests failed to detect infections in mothers of babies in whom congenital infection is demonstrated.

8.2.3 Specificity of IgM and IgG tests. Specificity of IgG tests can only be estimated in populations which are known to have not been exposed to the infection in question: this means that data collected in ZIKA-VT is not relevant to estimates of IgG specificity. However, IgM specificity can be studied by observing the relationship between the proportion of tests which are positive and the surveillance data over the previous 12 months. IgM persistence is believed to be about 12 weeks on average, so that an IgM+ occurring at a time when surveillance sources indicate there has been no virus circulating for over 4 or 5 months are highly likely to be false positives from a diagnostic point of view, whether due to persistent antibody, cross-reactions, or other factors; although it will be important to be able to rule out foreign travel before making these inferences. Data of this sort will be of great importance in defining the tails of the persistence distributions of IgM tests

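### Section 8.1.7 applies an incidence measured in IgG-negative women to an undefined N; if N is everyone and past infection protects, reporting is under-estimated and grossed-up infections over-estimated

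*SAP*

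**What the plan says.** In SAP Section 8, π is cumulative incidence, λ is incidence and θ(t) is the share of infections reported to surveillance. (Elsewhere the SAP also uses π and θ for infection timing and test persistence.)

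- **Section 8.1.4** estimates primary incidence from seroconversion: "The denominator is the number of women who were initially IgG- and who were retested on IgG at a later date". The rate follows: "Incidence of primary infection is found by dividing the number of seroconversions by total time at risk".
- **Section 8.1.6** gives a second route from rising seroprevalence: "then cumulative incidence at time t is related to incidence between t and T as follows", namely π(t) = π(T) + (1 − π(T))(1 − exp(−Σλ(u))).
- **Section 8.1.7** carries the result forward: "Once estimates of incidence are available, they can be aligned with surveillance reports to estimate the proportion of incident infections". The surveillance count M(t) is introduced with the words "cases are reported in, say, the population of adult women aged 16-44, over the same time period". The estimator is θ(t) = M(t)/[N(1 − e^(−λ(t)))], and N is explained only by "Where N is the relevant population size". θ(t) is presented as the reported share of all infections. It is to be inspected for stability over time, used in the adjustments of Sections 5 and 7, and used to gross up counts as M(t)/θ(t).
- **Section 8.2.1** proposes that "estimates of the average persistence of IgM can be estimated by dividing IgM prevalence by IgM incidence". The prevalence comes from Section 8.1.5, whose denominator is every woman ever tested for IgM. The incidence comes from Section 8.1.4 or 8.1.6.

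**The concern.** The same λ is used in two ways. In Sections 8.1.4 and 8.1.6 it is a hazard that acts on women not yet infected. In Section 8.1.7 it multiplies N with no allowance for women already infected. If N is the full population, the denominator counts infections that could not occur in women already immune.

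Three uses are exposed. Objective 2.2(iii), population estimates of infection, is delivered by M(t)/θ(t). The only planned check on θ(t), whether it stays stable, would confuse growing immunity with falling reporting. Section 8.2.1 sets a prevalence in all tested women against an incidence in susceptible women.

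The caveat that opens Section 8.1, that study incidence is not a true population figure, concerns recruitment from higher-risk areas and seasons. It does not deal with susceptibility.

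**Working it through.** The SAP prints no figure here, so the check sets the Section 8.1.7 formula against the Section 8.1.6 model.

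**Inputs.** From the SAP: the two formulas. Assumed, because the SAP gives none: N = 100,000, true reporting fraction θ0 = 0.10, λ = 0.105 for the period, and π at the start of the period from 0 to 0.7.

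**Step 1, algebra with no reinfection.** By Section 8.1.6, new infections are N[π(t) − π(T)] = N(1 − π(T))(1 − e^(−λ)).

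Reported cases are M = θ0 × N(1 − π(T))(1 − e^(−λ)).

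Section 8.1.7 then returns M/[N(1 − e^(−λ))] = θ0(1 − π(T)).

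Grossing up returns M/θ = N(1 − e^(−λ)), which is the true number divided by 1 − π(T).

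**Step 2, numbers.** 1 − e^(−0.105) = 0.09968, so the grossed-up figure is 9,968 in every row.

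| π at start | True infections | M | θ from 8.1.7 | Grossed-up / true |
|---|---|---|---|---|
| 0 | 9,968 | 996.8 | 0.100 | 1.00 |
| 0.1 | 8,971 | 897.1 | 0.090 | 1.11 |
| 0.3 | 6,977 | 697.7 | 0.070 | 1.43 |
| 0.5 | 4,984 | 498.4 | 0.050 | 2.00 |
| 0.7 | 2,990 | 299.0 | 0.030 | 3.33 |

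The last column is the same at λ = 0.01 and λ = 0.5, so in this model the ratio does not depend on λ.

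**Step 3, stability check.** Hold true reporting at 0.10, start from π = 0 and assume λ = 0.3 per period. π at the start of successive periods is 0, 0.259, 0.451, 0.593, 0.699. θ from Section 8.1.7 is 0.100, 0.074, 0.055, 0.041, 0.030. Reporting appears to fall although it is constant.

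**Step 4, reinfection allowed.** Let IgG-positive women have hazard rλ, with their infections reported at the same rate. The over-count becomes (1 − e^(−λ)) / [(1 − π)(1 − e^(−λ)) + π(1 − e^(−rλ))]. With λ = 0.105:

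| r | π = 0.3 | π = 0.7 |
|---|---|---|
| 0 | 1.43 | 3.33 |
| 0.5 | 1.17 | 1.52 |
| 1 | 1.00 | 1.00 |
| 1.5 | 0.88 | 0.76 |

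So 1/(1 − π) is an upper bound while r ≤ 1, and the direction reverses when r > 1.

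**Step 5, which π to use.** In Section 8.1.6, π(t) already includes the period's own infections: 1 − π(t) = (1 − π(T))e^(−λ). A correction using 1 − π(t) would inflate θ by e^λ, which is 5% at λ = 0.05 and 11% at λ = 0.10. The value at the start of the period is needed.

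**Step 6, Section 8.2.1.** With mean IgM duration d and primary infections only, IgM prevalence in all women is approximately λ(1 − π)d. Dividing by λ gives d(1 − π), which is too short. IgM-positive results from secondary infections push the ratio the other way.

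**The case against.** **N could mean the susceptible number.** The women aged 16-44 are named, as an example, for where M(t) is counted, not as the definition of N. For a hazard measured in IgG-negative women, the relevant population could be those still at risk, and the formula would then be correct. This stands as an ambiguity. The text never says it, though, and the only population offered is not restricted by serostatus, so whole-population N is the likelier reading.

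**The factor is not general.** A reader might infer that grossed-up totals are too high by 1/(1 − π) for all three viruses. The document does not support that. It expects secondary infections and previous infection with the same virus, and Step 4 shows how these shrink or reverse the bias. DENV is where Section 8.1.6 hints at high π, because the virus has been present longer, and it is also where the no-reinfection assumption is weakest. This objection stands.

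**The vertical transmission rate.** A reader might infer that the main estimate is biased, since θ(t) feeds the absolute risk used in Sections 5 and 7. Within the same centre and period, M/(θN) returns 1 − e^(−λ), the correct risk for a susceptible woman, so the error cancels for her. It would remain for women of unknown or positive prior serostatus, or where θ is carried to another place or time. Appendix 2 illustrates only a single sample and leaves the treatment of test sequences to be determined. An effect on the rate is therefore possible but not shown.

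**Section 8.2.1 is supportive only.** The SAP names Section 7.5 as the definitive source on persistence and plans separate primary and secondary estimates where avidity testing allows. That limits the weight of this part.

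**Conclusion.** The mismatch is real and internal to the SAP: Section 8.1.6 carries the susceptible fraction and Section 8.1.7 omits it for the same λ. Under two conditions, that N is the whole population and that past infection protects, θ(t) is low by 1 − π and M(t)/θ(t) is high by 1/(1 − π). The error is nil at π = 0, as at the start of an epidemic of a new virus, and reaches a factor of 2 at π = 0.5. These sizes rest on assumed π. For national grossing-up, the π that matters is that of the area where θ was estimated.

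The apparent decline in θ(t) under constant reporting follows from the same two conditions. Where repeat infection occurs, neither the size nor the direction is fixed, but the formula still pairs a primary-infection hazard with a quantity described as covering all infections.

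This should be fixed. It bears on objective 2.2(iii), which Section 2 places outside the main objectives.

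**What to change.** 1. In Section 8.1.7, write θ(t) = M(t)/{N[1 − π(start of period t)](1 − e^(−λ(t)))}, or define N as the number susceptible at the start of the period. Take π from Sections 8.1.2 and 8.1.6. In the Step 2 example with π = 0.5 this returns θ = 0.10 and 4,984 infections, against 0.05 and 9,968.
2. For viruses with repeat infection, restrict θ and M(t) to primary infections where these can be identified, or add a term for infections in IgG-positive women.
3. Where the θ-based risk serves as a prior for a woman of unknown serostatus, multiply the susceptible risk by her probability of being susceptible.
4. In Section 8.2.1, divide IgM prevalence from primary infections in all tested women by λ(1 − π), or restrict prevalence and incidence to the same population.

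The cost is a few lines of wording and one term that the plan already estimates. Intervals will be slightly wider because uncertainty in π is carried through.

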#### 8.2 Analyses of properties of diagnostic tests

As noted earlier the ZIKA-VT and ZIKA-VID programs are inter-related and the analyses set out in *Section 7.5* will provide the definitive information on the persistence of IgM and other tests.

However, the population epidemiology data collected by ZIKA-VT also provides an opportunity for *supportive* analyses of test persistence, sensitivity and specificity. Results should be compared with the more formal evaluations undertaken as part of ZIKA-VID, which will comprise evidence from published literature as well as findings from *de novo* field work.

8.2.1 Average persistence of IgM. Given estimates of IgM prevalence (section 8.1.5) and incidence of primary infections based on seroconversion (section 8.1.4) or changes in cumulative incidence (section 8.1.6), estimates of the average persistence of IgM can be estimated by dividing IgM prevalence by IgM incidence.

We anticipate that IgM persistence may differ in women with previous ZIKV or DENV infections. If these women can be identified by avidity tests it will be possible to generate separate estimates of average IgM persistence for primary and secondary infections

8.2.2 Sensitivity and cross-reactivity of IgM and IgG tests. Estimates of sensitivity will be available for IgM and IgG tests in women with infections confirmed by PCR, and from cases where tests failed to detect infections in mothers of babies in whom congenital infection is demonstrated.

8.2.3 Specificity of IgM and IgG tests. Specificity of IgG tests can only be estimated in populations which are known to have not been exposed to the infection in question: this means that data collected in ZIKA-VT is not relevant to estimates of IgG specificity. However, IgM specificity can be studied by observing the relationship between the proportion of tests which are positive and the surveillance data over the previous 12 months. IgM persistence is believed to be about 12 weeks on average, so that an IgM+ occurring at a time when surveillance sources indicate there has been no virus circulating for over 4 or 5 months are highly likely to be false positives from a diagnostic point of view, whether due to persistent antibody, cross-reactions, or other factors; although it will be important to be able to rule out foreign travel before making these inferences. Data of this sort will be of great importance in defining the tails of the persistence distributions of IgM tests

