### 7.5 Using ZIKA-VT data to update prior information on test persistence

The previous section has shown how, given information on test persistence, the date of a positive PCR or IgM test informs the GA of maternal infection. In this section, we show how to estimate the distribution of test persistence from ZIKA-VT data, or, more usefully, how to update any prior information available.

Simplifying assumptions have been made for purposes of clarity and in order to keep the notation minimal: for example, that the date of onset of symptoms is taken to be the date of the onset of infection, and that tests are positive from that date. Adjustments can, and will, be made to accommodate these factors, but at this stage greater veracity would be at the expense of clarity.

 $F(d,\theta)$  is defined for d=1,2...D where D is the maximum possible duration of that marker. The data generated by ZIKA-VT and similar studies is *doubly interval censored*, because in most cases neither the onset of the marker response, nor the end of the marker response, is observed. Methods for analysis of doubly interval censored data have been published [5, 6] and have been applied to the timing of maternal infection in the context of congenital toxoplasmosis [7, 8]. A recent paper [9] includes a brief up-to-date review of the most commonly used methods.

ZIKV and the ZIKA-VT protocol have features that require extensions and modifications to existing methods. First, not only is incidence changing over time, but each individual woman is exposed to a different incidence which varies over the course of her pregnancy. Second, information on multiple markers in multiple types of samples will need to be processed simultaneously.

We begin with an analysis for a single marker, then we consider how to handle variables that might affect persistence, such as previous infection or the presence of symptoms, and finally the joint analysis of multiple markers.

[figure not shown]

Author: [name] (UNIVBRIS)

21

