#### 8.1 Analyses to be carried out

Note that the estimates of incidence and seroprevalence that can be generated directly from ZIKA-VT are not true population estimates, because, within each collaborating center, the intention is to recruit pregnant women from areas at higher risk of arbovirus infection, and during periods of higher incidence. However, there is an interest in estimating incidence because it may correlate with risk of transmission or adverse clinical outcomes, if for example, both are related to viral load or degree of susceptibility.

All analyses will be initially stratified by center and mosquito season, or by center and year if there is no mosquito season. The text under each heading below should be understood as specifying one or more tables, in most cases separately for each of the three arboviruses.

8.1.1 Basic demographics of the sampled population. We will tabulate the numbers recruited each season, their age distribution. Further breakdowns will be by: socio-economic class, income range, type of housing, area of residence, residence stratified by arbovirus infection incidence (from surveillance data), as considered appropriate

8.1.2 Seroprevalence and cumulative incidence. For each arbovirus, the denominator for a seroprevalence estimate is the number of women who had at least one IgG test, and the numerator is the number who were IgG+ on their first test. In addition to "crude" (without adjustment) estimates of seroprevalence, we will obtain estimates of cumulative incidence  $\pi$ , which is (observed) seroprevalence p adjusted for IgG sensitivity and specificity, using the relationship

$$p = \pi Se + (1 - \pi)(1 - Sp)$$

Author: [name] (UNIVBRIS)

26

The sensitivity and specificity will be characterized as probability distributions based on the data available, assembled under the ZIKA-VID work package. The sources of this data will be continually updated (see *Appendix 4*).

If more than one test was used, results will be reported separately for each test (see Table 5)

The adjustment can be extended to account for cross-reactivity between DENV and ZIKV IgG tests, given information on sensitivity, general false positive rates, and cross-reactivity of both assays:

$$p_{Z} = \pi_{Z} S e_{Z} + (1 - \pi_{Z})(1 - S p_{Z}) + \pi_{D} X r_{Z}$$

$$p_{D} = \pi_{D} S e_{D} + (1 - \pi_{D})(1 - S p_{D}) + \pi_{Z} X r_{D}$$

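### Section 8.2.1 divides IgM prevalence by incidence to get mean IgM persistence, without the stable-incidence or complete-wave condition, matched times and matched denominators that the ratio needs

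*SAP*

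**What the plan says.** SAP section 8.2.1 takes IgM prevalence from 8.1.5 and the incidence of primary infection from 8.1.4 or 8.1.6, and states that "estimates of the average persistence of IgM can be estimated by dividing IgM prevalence by IgM incidence". It gives no condition on the course of incidence, no time window and no lag. It adds that separate averages may be produced for primary and secondary infections if avidity tests can identify them.

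The inputs are defined as follows.
- **Prevalence (8.1.5):** the denominator is every woman ever tested by IgM, and "the numerator is the number whose first IgM test was a +ve".
- **Incidence (8.1.4):** among women initially IgG-negative and later retested, "Incidence of primary infection is found by dividing the number of seroconversions by total time at risk".
- **Incidence (8.1.6):** the rate λ in the cumulative-incidence equation, which acts on the fraction not yet infected, 1 − π.

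Two other statements bear on the ratio. Section 7.5, explaining why existing persistence methods need extension, says "not only is incidence changing over time, but each individual woman is exposed to a different incidence". Section 8.1 says the intention is to "recruit pregnant women from areas at higher risk of arbovirus infection, and during periods of higher incidence", and that "All analyses will be initially stratified by center and mosquito season" (by center and year where there is no mosquito season).

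Section 8.2 calls its own analyses supportive, treats section 7.5 as the definitive source on persistence, and asks for comparison with the ZIKA-VID evaluations.

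**The concern.** IgM prevalence at a given time is made up of past infections, each weighted by the chance that the marker is still present. Dividing by incidence gives the mean duration when past incidence equals present incidence. In a rising epidemic there are too few old infections still positive for the current incidence, and the ratio is too small. In a falling epidemic it is too large. The SAP recognises changing incidence in 7.5 and models it there, but 8.2.1 makes no allowance for it.

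Two features of the inputs add to this. Prevalence at the first test looks back, whereas 8.1.4 incidence accrues afterwards, so the two describe different stretches of the epidemic. Prevalence is also a proportion of all tested women, whereas the incidence is a rate among those without earlier infection.

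At stake is the value of 8.2.1 as a comparison. A ratio that depends on when women were recruited could suggest a conflict with ZIKA-VID where none exists, or agreement where there is none. It could also produce an artificial difference between primary and secondary infections if the two groups fall at different points of the epidemic curve.

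**Working it through.** The SAP reports no figure from this estimator, so there is nothing to reproduce. The check asks what the rule returns when the answer is known.

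**Inputs.** From the SAP: a true mean of 12 weeks (8.2.3 gives about 12 weeks on average). Assumed: a single Gaussian wave of incidence with SD 5, 8 or 12 weeks and no endemic baseline; Weibull persistence with shape 1.5; even recruitment over each window.

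**Formula.** With I(u) the new infections per woman in week u and S(d) = 1 − F(d) the marker survival function,

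P(t) = Σ over u ≤ t of I(u)·S(t − u).

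**Step 1: constant incidence.** P = I × ΣS(d) = 12·I, so P/I = 12.0, as intended.

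**Step 2: exponential growth or decline.** Suppose incidence doubles every 4 weeks, so r = ln 2/4 = 0.173 per week.
- Exponential persistence: P/I = 1/(1/12 + 0.173) = 3.9 weeks.
- Fixed 12-week persistence: P/I = (1 − e^(−12r))/r = 0.875/0.173 = 5.05 weeks.
- If incidence halves every 4 weeks instead, fixed persistence gives (e^(12r) − 1)/r = 7/0.173 = 40 weeks.

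**Step 3: Gaussian wave, same-time ratio (weeks; truth 12).**

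| Window | SD 5 | SD 8 | SD 12 |
|---|---|---|---|
| Single week, 8 weeks before peak | 2.3 | 4.3 | 6.5 |
| Single week, at peak | 5.3 | 7.2 | 8.9 |
| Single week, 8 weeks after peak | 25.9 | 15.2 | 13.0 |
| Pooled within 1 SD of peak | 5.9 | 7.9 | 9.5 |
| Pooled, 26-week season centred on peak | 8.8 | 8.9 | 9.6 |
| Pooled, 52-week year centred on peak | 11.5 | 11.2 | 11.0 |
| Complete wave, total over total | 12.0 | 12.0 | 12.0 |

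With exponential, gamma (shape 3) or fixed persistence and SD 4 to 12, the 26-week pooled ratio is 7.6 to 10.9.

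**Step 4: the timing of the SAP's own inputs.** First-test prevalence is averaged over the same 26-week season and divided by mean incidence in the 26 weeks after each test. The ratio is 17.4, 16.2 and 14.8 weeks for SD 5, 8 and 12. The direction is reversed, because follow-up runs into the decline.

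**Step 5: denominators.** Let a fraction π of women already be infected, incidence be constant, and only primary infections raise IgM. New infections per woman are then λ(1 − π), so P/λ = 12(1 − π).
- π = 20%: 12 × 0.8 = 9.6 weeks.
- π = 50%: 12 × 0.5 = 6.0 weeks.
- π = 80%: 12 × 0.2 = 2.4 weeks.

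This error arises even in a steady state. Steps 4 and 5 pull in opposite directions. As a rough product at π = 50%, 14.8 to 17.4 becomes 7.4 to 8.7 weeks. The net sign therefore cannot be stated from the SAP alone.

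**The case against.** The strongest reply is that little depends on 8.2.1. Section 8.2 labels it supportive. Section 7.5 is definitive and already averages over each woman's distribution of infection time. Priors for the persistence distribution come from published data, with conflict checked by removing the prior and by fit statistics. A reader might infer that a biased ratio would distort the persistence distribution, and through it gestational age at infection and the vertical transmission rate. The documents do not support that: nothing feeds the ratio into those models, and no rule lets it overturn them. This part of the reply stands.

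A second reply is that a steady state is not strictly required. Totals over a complete wave also return 12 weeks, and a 52-week stratum comes close at 11.0 to 11.5, so stratification by season or year can remove part of the error. This also stands, but the SAP does not specify complete-wave totals, and recruiting in high-incidence periods tends to cut off the post-peak tail they need.

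A third reply concerns size. A reader might take the single-week values of 2 to 26 weeks as the expected error. They are not, because the SAP plans pooled strata, and wave width, zero baseline and recruitment pattern are assumptions. With a constant baseline equal to half the wave's height and SD 8 to 12, the 26-week pooled ratio is 10.2 to 10.5. This is fair, and the pooled figures are the ones to use. It does not address the mismatch of times and denominators.

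**Conclusion.** The point holds for a supportive analysis. As written, 8.2.1 recovers mean IgM persistence only under roughly constant incidence over the preceding persistence period, or with complete-wave totals, and in either case with matched times and denominators. The SAP requires none of these, and its own account of changing incidence and high-season recruitment makes the first unlikely to hold.

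For a true mean of 12 weeks under the assumed wave:
- pooled over a 26-week season, about 9 to 10 weeks (20% to 27% low, from 9.6/12 and 8.8/12);
- within one SD of the peak, about 6 to 9.5 weeks (21% to 51% low);
- first-test prevalence over later incidence, about 15 to 17 weeks (23% to 45% high).

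The denominator mismatch lowers the ratio further by the factor 1 − π if only primary infections raise IgM. These sizes rest on the assumed wave, persistence shape and even recruitment. That the ratio depends on recruitment timing does not. The consequence is an unreliable comparison with ZIKA-VID, with no direct effect on the section 7.5 analysis.

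**What to change.** In 8.2.1, replace the ratio for primary infections with

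prevalence(t) = Σ over u ≤ t of λ(u)·(1 − π(u))·{1 − F(t − u)},

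with λ and π taken from 8.1.6 or from surveillance scaled as in 8.1.7, and solve for the mean by center and season, using a one-parameter F if the data are thin. The factor 1 − π(u) must be included: λ in 8.1.6 acts on women not yet infected, whereas 8.1.5 prevalence covers all women tested. Without it, Step 5 shows persistence would be underestimated wherever earlier infection is common.

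Handle secondary infections separately. Sections 8.1.4 and 8.1.6 give the incidence of primary infection only, so a secondary-infection average needs its own incidence. Alternatively, restrict the prevalence to primary infections with a matching denominator.

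Report the simple ratio only for a window in which incidence is documented as flat, or which spans a complete wave, with prevalence and incidence matched in time and denominator, and label it crude.

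The cost is a change of wording and a short calculation from quantities that 8.1.6 and 8.1.7 already plan to produce. No new data are needed for the primary-infection estimate.
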